For cervical pessary therapy there is up to now only one cohort analysis¹⁹ for the combined risk factors available proving the placement of a cervical pessary to be as effective as cerclage or treatment with 200 mg vaginal progesterone in reducing preterm birth rate.

The risk factor 'history of at least one cold knife conisation' for PTB was up to now only addressed in a pilot study investigating the effect of pessary treatment in asymptomatic women with a singleton pregnancy along with a short sonographic cervix and it suggested a beneficial effect on the prolongation of the pregnancy⁷. A cervical pessary to support the cervix in pregnant women with cervical insufficiency was introduced in 1960. It is a silicone ring with a smaller diameter to be fitted around the cervix and a larger diameter to fix the device against the pelvic floor. This effectively rotates the cervix toward the posterior vaginal wall and corrects the cervical angle²⁰.

In approximately 1/3²¹ of pregnancies leading to PTB cervical shortening develops. Here the placement of a cervical pessary is a good therapeutic option. For this risk factor good evidence is available for cervical pessary treatment in singleton²² and twin pregnancies^{23, 24}. A Cochrane review²⁵ detailed a significant decrease in the incidence of spontaneous PTB in women with a short cervix when compared with expectant management: PTB less than 37 weeks' gestation (22% versus 59%; RR 0.36, 95% CI 0.27 to 0.49) and PTB less than 34 weeks' gestation (6% and 27% resp. RR 0.24; 95% CI 0.13 to 0.43).

This is the first RCT aiming to investigate the impact of a preventive cervical pessary therapy for the prevention of recurrent PTB in women with a history of PTB and/or history of at least one conisation.

Furthermore this RCT is a part of the first worldwide prospective metaanalysis in the medicine Global Obstetrics Network <http://www.globalobstetricsnetwork.org/projects/>

The primary outcome "Children's survival without neurodevelopmental disability at the age of 3 years" measures the long-time outcome of the intervention according to the CROWN²⁶ criteria.

Cervical pessary treatment is a non-invasive, well-tolerated and cost-effective treatment option²⁰ which could be easily implemented in daily practice if it proves to have a preventive effect of PTB. This especially applies for developing countries, where for example serial cervix length measurements to detect cervical shortening are not feasible.

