2.2. Description of the study population.

Women with a singleton pregnancy at 12 – 16 weeks of gestation and a history of at least one previous preterm delivery before 34+0 weeks and/or a history of previous cervical surgery attending the reference hospital and who do not fulfil the exclusion criteria the study will be proposed. The patients will be informed of the intended therapeutic effect and possible side effects. If they agree and after obtaining their informed consent, they will be randomised according to either usual management with rescue cerclage placement only when (and as soon as possible) a cervical shortening below 25 mm occurs (=control group) or cervical pessary placement (= pessary group).

Pessaries or cerclage shall be placed up to 37+0 weeks of gestation. In the control group serial cervical length measurements shall be conducted every 4 weeks in order to diagnose cervical shortening as soon as possible.

2.3. Name and description of the device under investigation.

The Arabin cervical pessary, which is CE-certified for preventing SPB (CE 0482 / EN ISO 13485: 2012 + AC:2012 annex III of the council directive 93/42 EEC).

See annex I.

2.4. Statement that testing will be performed according to protocol, GCP and applicable legal requirements.

The Clinical Trial will be conducted following the protocol, the GCP, and all legal requirements.

3. Objective

This study aims to investigate the benefit of a prophylactic cervical pessary treatment in women at high risk of PTB due to a history of at least one previous preterm delivery before 34+0 weeks and/or a history of previous cervical surgery on the children's long-term survival without neurodevelopmental disability.

Hereby, a standardized and validated test called 'Ages and Stages 3rd edition'²⁷ should evaluate the children's neurodevelopment. The test should be conducted by the parents and takes approximately 12 minutes. The questionnaires will be provided by the sponsor.

4. Design

4.1. Specific description of primary and secondary variables.

4.1.1. Primary outcome:

- Children's long-term survival without neurodevelopmental disability

4.1.2. Secondary outcomes:

- Offspring
 - Time to birth
 - Preterm birth before 37 weeks: rate of delivery before 36+6 weeks
 - Preterm birth before 34 weeks: rate of delivery before 33+6 weeks

Confidential

[figure not shown]
[figure not shown]
- Preterm birth before 32 weeks: rate of delivery before 31+6 weeks

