 - Preterm birth before 30 weeks: rate of delivery before 29+6 weeks
 - Preterm birth before 28 weeks: rate of delivery before 27+6 weeks
 - Birth weight: median weight (g) of the newborns at birth
 - Fetal or neonatal death: rate of intrauterine demise or neonatal death during the first 24 hours
 - Neonatal morbidity: rate of major adverse neonatal outcomes before discharge from the hospital
 - Intraventricular Haemorrhage (IVH): grades III-IV
 - Retinopathy of prematurity
 - Respiratory Distress Syndrome (RDS): grades II-IV,
 - Need for ventilation > 72 h
 - Necrotising enterocolitis
 - Proven or suspected sepsis, antibiotics (>5 days)
 - Need (Duration in days) for neonatal special care (NICU)
 - Harm from intervention
- Mother:
- Maternal death
 - Significant maternal adverse events (rate):
 - Heavy bleeding: bleeding that requires a medical intervention
 - Cervical tear: cervical rupture due to the pessary placement
 - Uterine rupture: rupture of the uterus due to contractions or surgery
 - Physical or psychological intolerance to pessary: discomfort or pain due to the pessary that makes daily life uncomfortable (number of cases)
 - Rupture of membranes before 32 weeks: rate of—rupture of amniotic membranes before 31+6 weeks
 - Infection/inflammation
 - Hospitalisation for threatened preterm labour before 32 weeks: requirement of hospitalisation due to preterm contractions that need medical treatment to try to stop them before 31+6 weeks (rate)
 - Mean hospital stay duration: number of days of admittance at the hospital
 - Use of tocolytic treatment: Type of tocolytic, days of treatment, dose

4.2. Description of the trial design.

Open Multicentre International Collaborative Randomized Controlled Trial, in parallel groups, based on intention-to-treat analysis comparing the placement of a prophylactic cervical pessary with usual management in singleton pregnancies at high-risk of PTB due to a history of at least one previous preterm delivery before 34+0 weeks and/or a history of previous cervical surgery.

4.3. Flowchart.

Confidential

4.4. Description of the medical device and the treatment regimen.

The cervical pessary is a vaginal device (silicone ring) that is used to treat pregnant women for preventing spontaneous preterm birth. This device can be easily placed around the uterine cervix without pain (see annex I).

Confidential

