Every center will receive a password and a username in order to access the database for recruitment, randomization and documentation of patient data. Hereby, a personal identification number will be assigned for every patient. Patient names will not appear in the databases.

This database will be supervised and coordinated by PD [name], Bürgerhospital Frankfurt/M. (Webmaster).

4.8. Identification of data to be collected in the case report files (CRF) that should be considered as data source.

Data will be collected in E-CRF, provided by >[name] Wissenschaft, Berlin< on study software "Castor".

4.9. Definition of what is considered to be the end of the study.

The study will be finished after the 3 year-follow up examination of the surviving children focusing on neurodevelopmental disabilities.

5. Selection and withdrawal of subjects

5.1. Inclusion criteria.

- Women with a singleton pregnancy and a history of at least one previous preterm delivery before 34+0 weeks and/or a history of previous cervical surgery
- 12+0 -16+0 weeks of gestation
- Minimal age of 18 years
- Informed consent signature

5.2. Exclusion criteria.

- Major fetal abnormalities (requiring surgery or leading to infant death or severe handicap)
- Cerclage prior to randomisation
- Uterine malformation
- Placenta previa totalis
- Active vaginal bleeding at the moment of randomization
- Spontaneous rupture of membranes at the time of randomization
- Silicone allergy
- Painful regular uterine contractions
- Current participation in another RCT

5.3. Withdrawal criteria.

If a participant may voluntarily withdraw from treatment or if it is necessary to remove the pessary due to the conditions described before, the patients will be followed as usual until delivery (intention-to-treat analysis).

Replacement of patients is not applicable in this trial.

5.4. Rescue treatment criteria.

Regarding the control group, a McDonald cerclage may be indicated if there is a cervical shortening below 25 mm during the follow-up scans according to the current guidelines and expert recommendations¹¹.

6. Treatment of Subjects

6.1. Treatments to be administered.

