(2) The primary outcome will be evaluated 3 years after the last woman enrolled in this study has delivered her neonate.

Confidential

A descriptive analysis by preterm birth will be carried out calculating means and medians for quantitative variables and proportions with 95% confidence intervals for categorical variables.

Additionally we will perform an explorative subgroup analysis of the study collective comparing the efficacy of the cervical pessary treatment in women with a normal cervical length at 12 -16 weeks of gestation and in women who have developed a cervical shortening (< 25 mm) as an additional risk factor.

For the primary endpoint we expect to have a drop out rate of up to 25% due to the long follow-up time (3 years) of the study; but we do not expect to have lost data for the secondary endpoints because for these parameters the study has a short follow-up time till time to birth only.

An interim analysis shall be conducted on key safety parameters after birth of 150 neonates: the following safety endpoints will be assessed by a one-sided test with $\alpha=1\%$

- on level of the neonates:

rate of preterm birth, time to birth, birth weight, death, neonatal morbidity, harm of intervention

- and on the maternal level:

rate of hospitalisation for threatened preterm labour < 32 weeks, rate of P_{RoM} <32 weeks, rate of infection / inflammation, rate of physical or psychological intolerance to pessary, rate of SAR/SAE, death.

The trial will be terminated as negative if a disadvantage for the pessary-treatment can be found in one of these tests. To guarantee a high safety level the significance level is chosen more conservatively than in a Bonferroni correction. All analysis will be carried out with SPSS® version 19.0 or later (IBM Company SPSS Inc.

Headquarters, Chicago, Illinois, USA) and R version 3.2.3 or later (R Foundation for Statistical Computing, Vienna, Austria).

Primary Outcome	Statistical Test
Children`s Long-Term Survival without Neurodevelopmental Disability (3-Years-follow up)	Chi-Square test
Secondary Outcome	Statistical Test
Birth before 34 Weeks of Gestation	Chi-Square test or Fisher test
Time to Birth	Cox regression
Birthweight	t-test or Wilcoxon-Mann-Whitney test
Fetal / Neonatal Death	Chi-Square test or Fisher test
Neonatal Morbidity	Chi-Square test or Fisher test
Need for Hospitalization	Chi-Square test or Fisher test
Days of Hospitalization	t-test or Wilcoxon-Mann-Whitney test

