Maternal Adverse Events	Chi-Square test or Fisher test
Pessary Intolerance	Chi-Square test or Fisher test
Vaginal Infections	Chi-Square test or Fisher test

9.2. Expected number of subjects to be included.

For sample size calculation, we assume a combined event rate for the primary outcome (long-term survival without neurodevelopmental disability at 3 years of follow up) of 8% for the pessary group (see van't Hooft, Pro Twin Trial²⁸) and an event rate of 20% for the control group. Group sample size of 121 in both groups achieve 80% power to detect this difference using a two-sided chi-square test with significance level $\alpha=5\%$. To account for a drop out rate around 15%, sample size of 155 in each group, overall n=310 women will be recruited.

9.3. Criteria for termination of the trial.

A non-justified case of maternal death (temporary stop until complete evaluation of the case by an external committee).

9.4. Selection of subjects to be included in each analysis.

The analysis will include all the subjects that have been randomised.

10. Direct Access to Data Source

Direct access will be granted to the authorized monitor, host institution and the regulatory authorities to permit trial-related monitoring, audits and inspections.

11. Quality and Control Assurance

Main investigator and collaborators: In order to ensure the Quality of the data they will provide instructions and training to the sites involved in the trial; review the CRF data; and detail of any other steps taken to ensure quality of research.

The main investigator will sign the study protocol and the “investigator’s commitment; he will apply for the Ethics Committee and the Director’s approval; and he will review the final report of the study.

The collaborators will assess patient’s eligibility, they will inform the patients and ask for the informed consent; and they will be responsible of the CRF and obtaining and registering all data.

Monitor: he will perform regular monitoring according to ICH GCP. Data will be evaluated for compliance with the protocol and accuracy in relation to source documents. Monitors will verify that the clinical trial is conducted and data are generated, documented and reported in compliance with the protocol, GCP and the applicable and local regulatory requirements.

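### The interim rule can end the trial as negative on pessary intolerance alone, an event that only the pessary arm can record

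*Combined protocol and SAP*

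**What the plan says.** Section 9.1 of the combined protocol and SAP sets one interim look: "An interim analysis shall be conducted on key safety parameters after birth of 150 neonates". It lists six neonatal and six maternal endpoints, each to be assessed one-sided at 1%. The maternal list ends with "rate of physical or psychological intolerance to pessary, rate of SAR/SAE, death". The consequence is stated without qualification: "The trial will be terminated as negative if a disadvantage for the pessary-treatment can be found in one of these tests".

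Section 4.1.2 defines the endpoint: "Physical or psychological intolerance to pessary: discomfort or pain due to the pessary that makes daily life uncomfortable (number of cases". The control arm receives no pessary by design. Under sections 4.4 and 5.4 these women have serial cervical length scans, with cerclage for a short cervix.

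The interim text names no test. The table of tests in section 9.1 gives chi-square or Fisher for "Pessary Intolerance", as for the other binary secondary outcomes. No expected intolerance rate is given. The only statement on tolerability is in the rationale (section 2): "Cervical pessary treatment is a non-invasive, well-tolerated and cost-effective treatment".

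**The concern.** A one-sided 1% test limits wrongful stopping only if the two arms could have equal rates. Here they are equal only if no pessary woman reports the event at all. Any real frequency of discomfort makes the null false, and whether the boundary is crossed then depends on how common discomfort is and how many women have been counted. The test does not compare the pessary with standard care on anything both arms can experience.

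The consequence is out of proportion to the signal. The trial would be closed as negative, although the result would carry no information on preterm birth, neonatal morbidity or the 3-year primary outcome. Section 9.1 puts no review step between this signal and termination. Section 4.9 says "The study will be finished after the 3 year-follow up examination of the surviving children", but the documents do not say whether children already born would still be followed to age 3 after an interim stop. The primary outcome could be lost.

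**Working it through.** The plan gives no event count for this boundary and no expected rate, so there is no figure of its own to reproduce.

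**Inputs**
- 150 births in singleton pregnancies, hence 150 women (sections 9.1 and 5.1).
- One-sided 1% per endpoint; any single significant test ends the trial (section 9.1).
- 75 women per arm: an assumption, from the equal planned groups of 155 (section 9.2).
- 0 control cases: follows from the definition in section 4.1.2 and a control arm without pessaries.
- Test: chi-square or Fisher from the table in section 9.1. The interim text names neither, so the Yates-corrected chi-square is shown as well.
- True intolerance rate: not in the documents; assumed between 2% and 15%.

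**Step 1: cases needed to stop**

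For x of 75 against 0 of 75, with pooled proportion p = x/150:
- Chi-square: z = (x/75) / √[p(1−p)(2/75)]. At x = 6: 0.08 / √(0.04 × 0.96 × 2/75) = 0.08/0.032 = 2.50, one-sided p = 0.0062.
- Fisher: p = C(75,x)/C(150,x). At x = 7 this is 0.0067.
- Yates: subtract ½(1/75 + 1/75) = 0.0133 from the difference. At x = 8: z = 2.54, one-sided p = 0.0055.

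| Pessary cases | Chi-square | Fisher | Yates |
|---|---|---|---|
| 5 | 0.0115 | 0.0292 | 0.0344 |
| 6 | **0.0062** | 0.0141 | 0.0186 |
| 7 | 0.0034 | **0.0067** | 0.0101 |
| 8 | 0.0018 | 0.0032 | **0.0055** |

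The rule fires at 6, 7 or 8 cases, that is 8.0%, 9.3% or 10.7% of the pessary women.

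**Step 2: chance of stopping on this test alone**

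P(X ≥ boundary) with X ~ Binomial(75, true rate):

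| True rate | Boundary 6 (chi-square) | Boundary 7 (Fisher) | Boundary 8 (Yates) |
|---|---|---|---|
| 2% | 0.4% | 0.08% | 0.01% |
| 3% | 2.5% | 0.7% | 0.2% |
| 5% | 17% | 8.1% | 3.4% |
| 10% | 77% | 63% | 48% |
| 15% | 98% | 95% | 89% |

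The chance passes the nominal 1% once the true rate exceeds 2.4%, 3.2% or 4.0% (chi-square, Fisher, Yates). It reaches 50% at 7.5%, 8.9% or 10.2%.

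**Step 3: sensitivity**
- 70 pessary against 80 control: boundary 5, 6 or 7 (chi-square, Fisher, Yates).
- 80 against 70: boundary 6, 8 or 8.
- Over these splits and tests, the chance of stopping is 3.4% to 27% at a 5% rate and 48% to 84% at 10%. At 2% the largest value is 1.3% (70 against 80, chi-square).
- One control case, for example a control woman who was given a pessary: the boundary at 75 against 75 rises to 8, 9 or 10.

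**Step 4: the 1% level against Bonferroni**

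With 12 endpoints, 0.05/12 = 0.42%. If all five preterm-birth cut-offs in section 4.1.2 are tested, there are 16 tests and 0.05/16 = 0.31%. The chosen 1% is looser than either. Section 9.1's claim to be more conservative than Bonferroni can therefore only mean quicker to stop for harm.

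**The case against.** The strongest reply has four parts.

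First, the two-group test is inferred. The chi-square or Fisher row belongs to the table of secondary outcomes, and the interim text names no test. If a one-arm assessment was meant, the boundary of 6 to 8 does not follow. This is fair, but a disadvantage for the pessary implies a comparison, and a one-arm test would need a reference rate, which the plan does not give. Neither reading leaves a usable rule.

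Second, the size rests on assumed rates, and the device is described as well tolerated. This stands as a limit on the size: near 2% the problem is negligible. No figure supports that description, however, so 5% or 10% cannot be ruled out from the documents.

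Third, pain that impairs daily life is itself a harm, and for a preventive device a low stopping threshold may be intended. It is a harm and should be monitored. But if a low threshold is intended, it should be set as a tolerability limit. A test against a structural zero does not do that, and stopping on it does not make the trial negative for efficacy.

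Fourth, a data monitoring committee is named at the front of the protocol and could use judgement. Section 9.1 gives it no part in this rule. By contrast, section 9.3 provides a temporary stop with external evaluation even for a maternal death.

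**Conclusion.** The concern holds. As written, one of the tests that automatically end the trial compares the arms on an event that only one arm can have. Its 1% level gives no protection against stopping, and a positive result would not justify calling the trial negative.

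The trigger of 6 to 8 cases assumes a between-group test, 75 women per arm and no control cases; moderate imbalance moves it to between 5 and 8. How likely a stop is depends on an intolerance rate the documents do not state: negligible near 2%, appreciable at 5%, and about even or higher at 10%. The flaw should be corrected before the 150-birth look. The Bonferroni wording and the differing termination lists in sections 9.1 and 9.3 are minor and add nothing to the weight of this point.

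**What to change.** Before the interim look, remove pessary intolerance from the automatic termination tests in section 9.1 and add:

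> Pessary intolerance will be reported at the interim for the pessary arm only (number, percentage, 95% CI) and reviewed by the data monitoring committee; it is not a termination criterion.

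For example, 7 of 75 would be reported as 9.3% (exact 95% CI 3.8% to 18.3%). Keep the other interim endpoints and the 1% level.

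Two wording changes belong in the same amendment: say that 1% per test is deliberately quicker to stop for harm than a Bonferroni correction, and give sections 9.1 and 9.3 the same list of termination criteria.

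The cost is one fewer automatic trigger. High intolerance would lead to committee review instead of an automatic stop. Serious device harm is still tested through the SAR/SAE rate, but non-serious pain would no longer stop the trial by itself; the sponsor and the committee should accept that knowingly. A changed stopping rule is probably a substantial amendment needing ethics committee and regulatory approval under section 12. No new data or patients are needed.

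### Section 9.1 calls the interim level of 1% per test more conservative than Bonferroni, but for 12 tests it is laxer in the usual sense, its false-stop probability is unstated, and one of the tests has no valid null

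*Combined protocol and SAP*

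**What the plan says.** The interim safety analysis is described in section 9.1 of the combined protocol and SAP. It takes place once, after 150 neonates have been born.

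- **Tests.** The plan says that "the following safety endpoints will be assessed by a one-sided test with" a level of 1%.
- **Neonatal endpoints (six).** "rate of preterm birth, time to birth, birth weight, death, neonatal morbidity, harm of intervention".
- **Maternal endpoints (six).** "rate of hospitalisation for threatened preterm labour < 32 weeks", membrane rupture before 32 weeks, and then "rate of infection / inflammation, rate of physical or psychological intolerance to pessary, rate of SAR/SAE, death".
- **Decision rule.** "The trial will be terminated as negative if a disadvantage for the pessary-treatment can be found in one of these tests".
- **Justification.** In an opening clause that gives a high level of safety as the aim, the plan says that "the significance level is chosen more conservatively than in a Bonferroni correction".

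The section gives no Bonferroni level, no family level for the interim tests and no probability of stopping when the pessary does no harm. The general significance level in 9.1 is 5%. The table of tests in 9.1 allows chi-square or Fisher for binary secondary outcomes. Section 9.3 separately provides for a temporary stop and external evaluation after a non-justified maternal death.

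**The concern.** In ordinary use, a significance level that is more conservative than Bonferroni is smaller than the Bonferroni level, so that rejection is harder. With 12 tests, 1% is larger. A sponsor, ethics committee or monitoring committee reading the sentence in its ordinary sense would conclude that a false stop is better controlled than under Bonferroni, when it is less well controlled.

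A false stop would end the trial as negative on short-term endpoints, before the 3-year primary outcome is evaluated. Two related weaknesses lie in the same rule. One listed endpoint, intolerance to the pessary, can hardly arise in the control arm, so a difference between the arms is built in. And at this sample size a test on deaths has little chance of signalling, so a non-significant result could be mistaken for reassurance.

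**Working it through.** **Inputs.** From 9.1: 12 endpoints (6 + 6), one-sided 1% each, any one stops, one look at 150 births. Assumed: about 75 per arm, from the equal planned group sizes in 9.2; a 5% family level, the only general level given; and chi-square or Fisher at the interim, as in the table of tests.

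**1. The plan's comparison with Bonferroni.** The Bonferroni level is α/k = 0.05/12 = 0.42%. The plan's level is 1%, and 1/0.417 = 2.4 times as large. At a 5% family level, 1% is stricter than Bonferroni for four tests or fewer (0.05/4 = 1.25%), equal for five, and laxer from six upward (0.05/6 = 0.83%). The plan's statement, read in the usual sense, is not reproduced for 12 tests.

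**2. Chance of at least one false signal if every test has its full 1% size.**

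| Assumption | Probability |
|---|---|
| Upper bound, any dependence: 12 × 1% | 12% |
| Independent: 1 − 0.99^12 | 11.4% |
| Common correlation 0.2 (simulated) | 10.2% |
| Common correlation 0.4 (simulated) | 8.5% |
| Common correlation 0.6 (simulated) | 6.6% |
| Bonferroni level, independent: 1 − (1 − 0.05/12)^12 | 4.9% |

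Preterm birth, time to birth, birth weight and morbidity must be correlated, so the independent figure is an upper-end value. Leaving out intolerance gives 1 − 0.99^11 = 10.5% if independent.

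**3. Allowing for rare events.** Tests on uncommon binary events do not reach their nominal size. With 75 per arm and a 2% event, the one-sided size is 0.02% for Fisher and 0.09% for uncorrected chi-square. For maternal death it is close to zero. A patient-level simulation of 11 endpoints (maternal death omitted) gave a false-signal probability of about 3.5% to 6% with Fisher and about 5% to 9% with chi-square. Its event rates are assumptions, since the documents give none for the interim endpoints: preterm birth 25%, death 3%, morbidity 12%, harm 3%, hospitalisation 10%, membrane rupture 6%, infection 15%, intolerance 5%, serious events 20%, all varied from half to double.

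**4. Pessary intolerance.** With 0 of 75 in the control arm, one-sided Fisher gives p = 0.014 at 6 cases and p = 0.0067 at 7. So 7 of 75 stops the trial. The probability of 7 or more among 75 is 8% at an assumed true rate of 5%, 63% at 10% and 95% at 15%.

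**5. Deaths.** At 75 per arm a signal needs 7 v 0 by Fisher (p = 0.0067), or 6 v 0 by uncorrected chi-square (p = 0.006). If deaths rose from an assumed 3% to 6%, the test would signal with probability of about 3% (Fisher) or 5% (chi-square).

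**The case against.** The strongest reply is that the sentence opens by naming a high safety level as its aim. In a rule for stopping on harm, conservative can mean protective of patients, that is, quicker to stop. On that reading 1% against 0.42% is consistent and may be deliberate. This stands as a possible reading, so one should not infer that the sponsor believes false stops to be tightly controlled; the documents do not show that. What remains is that the sentence can be read in two opposite directions and that neither reading comes with a probability.

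A reader might also take 11% as the expected false-stop rate. It is not: it requires independent tests of full size, and discreteness and correlation bring it down. Nor do the documents support adding several preterm-birth cut-offs as independent tests. The interim list names one rate of preterm birth, and the cut-offs among the secondary outcomes are nested.

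A reader might further infer that the plan overlooks grave harm altogether. It does not. Section 9.3 covers maternal death case by case, section 8.3 requires notification of fatal or life-threatening events within 24 hours, and a data monitoring committee is named at the front of the protocol. The weakness of the significance test matters for fetal and neonatal death, for which 9.3 has no matching provision.

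Finally, a false harm stop does not inflate the type I error for efficacy. That is correct; the cost is the loss of the trial.

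**Conclusion.** The concern holds in a limited form. In the usual sense of a significance level, the comparison with Bonferroni is wrong for 12 tests by a factor of 2.4, given a 5% family level. In the protective sense it is true but unexplained. Either way the plan omits the figure needed to judge the rule. Under no harm, the chance of at least one false signal is at most 12%, 11.4% if the tests are independent and of full size, and more plausibly about 3.5% to 9%; that last range rests on assumed event rates and on the choice between Fisher and chi-square.

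Intolerance is a separate defect and possibly the larger one. It has no valid null between the arms, and under an automatic rule it could end the trial with a probability of about 63% at an assumed 10% rate. The documents give no expected intolerance rate, so that figure is an illustration of scale.

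The point should be addressed before the interim analysis. It does not affect the validity of the primary test.

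**What to change.** In section 9.1:

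1. Replace the sentence on Bonferroni with, for example: *Each test uses one-sided 1%, which is less strict than Bonferroni (0.42% for 12 tests at 5% overall), so that possible harm is flagged readily; the chance of at least one false signal is up to about 11% (11.4% if the tests are independent).* Adjust the count and the figure if intolerance is removed from the tests (11 tests: Bonferroni 0.45%, 10.5% if independent).
2. Make a 1% signal a trigger for review by the data monitoring committee rather than automatic termination.
3. Report pessary intolerance descriptively in the pessary arm, not as a between-arm stopping test.
4. Add that a non-significant comparison of fetal or neonatal deaths is weak evidence of safety, because about 75 per arm needs 7 v 0 by Fisher or 6 v 0 by uncorrected chi-square. Maternal death stays under 9.3.

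Moving to a Bonferroni level is not recommended. At 0.42%, Fisher would need 8 v 0 (p = 0.003), so the rule would see even less of the rare harms. Holm gives nothing extra, since its first step is Bonferroni and one rejection is enough to stop.

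The cost is wording only, with no change to sample size or data collection. The downside is a less favourable stated figure and a committee judgement in place of an automatic rule.
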